5.6. Handling of Missing Data

The missing data for Cognitive composite is discussed in Section 5.5.

For adverse events, where either the onset time or resolution time is unknown, time since first dose and duration will be imputed as follows:

- If onset date is unknown, and it cannot be confirmed that onset was prior to the start of dose administration, then the AE will be classified as treatment-emergent, with unknown time since first dose.
- If either the date of onset or the date of resolution is unknown, then duration will be shown as unknown.
- If onset time is unknown:
 - If the date of onset is known to be the date of first dose administration, and it is confirmed by a CRF comment or communication with the site that onset was prior to the start of dose administration, then the AE will be classified as not treatment-emergent.
 - If the date of onset is known to be same as the date of first dose administration, and it is confirmed by a CRF comment or communication with the site that onset was after the start of dose administration, then Time since first dose will be shown on the listing as “<1” day.
 - If the date of onset is known to be later than the date of first dose administration, then Time since first dose will be determined as the number of days since first dose, shown on the listing as “~n” days, where n is the number of days difference between the date of dose administration and the date of onset.
- If either the onset time or resolution time is unknown:
 - If the date of onset and the date of resolution are known to be the same, then Duration will be shown on the listing as “<1” day.

- If the date of onset and the date of resolution are known and are different, then Duration will be determined as the number of days difference between the date of onset and the date of resolution, shown on the listing as “~n” days.

Baseline for safety assessments:

- Missing values for safety assessments will not be imputed. If change from baseline is to be determined and the pre-dose baseline assessment is missing, then the previous scheduled result (e.g. Screening or Day -1) will be used as the baseline. However, if the baseline is missing due to technical reasons and a subsequent unscheduled pre-dose assessment is used to confirm eligibility, this unscheduled assessment may be used as baseline.

Pharmacokinetic concentration and collection times:

- Missing PK concentrations will not be imputed, except:
 - If the Day 1 pre-dose concentration is missing and the analyte is not endogenous, then a value of zero will be imputed;

Efficacy missing data rules:

- The ADAS-Cog11 total score ranges from 0-70 with higher scores indicating greater dysfunction. When the total score is missing due to non-cognitive reasons for one of the questions, the total score will be calculated as a weighted average of the scores provided for the remaining ten questions as follows:
 - $\text{Imputed Total} = \text{Observed Total Score} * (1 + \text{Maximum Score of the missing value} / \text{Sum of the Maximum Score of the non - missing values})$

Calculation of Imputed ADAS-Cog-11 Total Score

Missing Question	Imputed Total formula
Word Recall	$\text{Observed Total} * (1 + 10/60)$
Orientation	$\text{Observed total} * (1 + 8/62)$
Word Recognition	$\text{Observed total} * (1 + 12/58)$
All other questions	$\text{Observed total} * (1 + 5/65)$

In cases where 2 or more questions are missing, the total score will not be imputed and will be set to missing.

- The ADAS-Cog-13 total score ranges from 0-85. The imputed total score when there is only one item is missing due to non-cognitive reasons is presented below:

Calculation of Imputed ADAS-Cog-13 Total Score

Missing Question	Imputed Total formula
Word Recall	Observed Total*(1+10/75)
Orientation	Observed total*(1+8/77)
Word Recognition	Observed total*(1+12/73)
Delayed Word Recall	Observed total*(1+10/75)
All other questions	Observed total*(1+5/80)

- The ADAS-Cog-14 total score ranges from 0-90. The imputed total score when there is only one item is missing due to non-cognitive reasons is presented below:

Calculation of Imputed ADAS-Cog-14 Total Score

Missing Question	Imputed Total formula
Word Recall	Observed Total*(1+10/80)
Orientation	Observed total*(1+8/82)
Word Recognition	Observed total*(1+12/78)
Delayed Word Recall	Observed total*(1+10/80)
Maze	Observed total*(1+12/78)
All other questions	Observed total*(1+5/85)

- No further imputation for efficacy assessments. In order to have all subjects with any non-missing efficacy data contributing to the analysis, a mixed model for repeated measures (MMRM) will be used to take the missing data into account. Under the assumption that missing data are missing at random, inferences based on methods of MMRM estimation in mixed models are valid.

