- Baseline for ADAS-Cog11, ADAS-Cog13, ADAS-Cog14, NTB, ADCS-ADL, MMSE, CDR-SB, and ADCS-CGIC will be the most recent scheduled assessment prior to first dose

Efficacy Assessments:

- MMSE Total Score = sum of the individual scores from the 11 questions on the scale.
- The ADAS-Cog11 total score = the sum of all 11 individual items (word recall; commands; constructional praxis; naming objects and fingers; ideational praxis; orientation; word recognition; remembering test instructions; spoken language; word finding; and comprehension of spoken language). The ADAS-Cog 11 will be considered the primary cognitive endpoint for this study.
- The ADAS-Cog13 total score includes all of the items in the ADAS-Cog11 and the delayed word recall and the number cancellation.
- The ADAS-Cog14 total score includes all of the items in the ADAS-Cog13 and the maze item.
- The Cognitive Composite score will be calculated using z-scores of the below items. The z-scores will be derived by calculating the baseline mean and standard deviation of each individual component for all subjects. A z-score within each component will be derived for each subject at each timepoint by subtracting the corresponding baseline mean and then dividing by the corresponding baseline SD. The Cognitive Composite score will be set as the mean of the 10 individual z-scores within each subject and timepoint. If a subject is missing one, two, or three scores at a particular timepoint, the missing scores will be set as the average non-missing z-score of all subjects at that timepoint within each component when deriving the Cognitive Composite score. If a subject is missing four or more individual components at each timepoint, the Cognitive Composite score will not be derived.

ADAS-COG

Word recall (scored on a 0 to 30 range), sum of trials I, II, and III. If at least one of the trials is missing, this component will be considered missing. The sign of the z-score for this component will be reversed when deriving the Cognitive Composite score as it is the total words not recalled that is being recorded. This test is a key measure of episodic memory.

Orientation (0 to 8). The sign of the z-score for this component will be reversed when deriving the Cognitive Composite score as the recorded score for this test is the number of items answered incorrectly. This measure is an index of the study participant's episodic memory and a single item of semantic memory (their name).

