Delayed Word Recall (0 to 10). The sign of the z-score for this component will be reversed when deriving the Cognitive Composite score as it is the total words not recalled that is being recorded.

Word Recognition (0 to 24). The sign of the z-score for this component will be reversed when deriving the Cognitive Composite score. This is a further test of episodic memory using a word recognition paradigm of 12 true positive targets and 12 foil items. While the possible score for this measure is 0 to 24, the standard ADAS-Cog score is capped at a maximum worst score of 12.

Number Cancellation (0 to c.40). This test was added to the original ADAS-Cog to remedy the absence of an attentional test. Performance can range between a score of 0 and c.40. ADAS-Cog scoring requires that ‘False alarms’ be subtracted from ‘hits’ to yield a score which is reported as 0 to 5 for ADAS-Cog scoring purposes. Having ensured that the total number of false alarms are comparable across both arms of the study, we will analyze total hits. If false alarms are unbalanced across study arms then the statistic ‘D’ will be calculated using Signal Detection Theory.

Maze - The ADAS-Cog14 augments the ADAS-Cog11 with delayed free recall, number cancellation, and maze-completion measures. A score of 0 to 10 for delayed free recall and a conversion code of 0 to 5 for the digit cancellation and maze completion provides total score ranges for the extended ADAS-Cog14 from 0 to 90. The Maze item will be included as one of the components when deriving the Cognitive Composite and Attention Composite score. The sign of the z-score for this component will be reversed when deriving these composite scores.

NTB

CFT – This is a further test of working memory and executive function that yields a key metric referred to as ‘Total number of acceptable words’. This is obtained by calculating how many of the study participant’s responses are deemed acceptable according to the scoring rules. The usual performance range for this test is between 0 and 40.

Digit Span – This is a brief measure of working memory, especially in the Digits Backwards section. The key metric is ‘Total number of trials correct’, which is the number of sequences correctly recalled. The range of the test is 0 to 24 and both floor and ceiling effects are rare.

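### SAP 5.6 prorates a missing Maze item with the Word Recognition factor (1+12/78) instead of 1+5/85, so the imputed ADAS-Cog14 total comes out 9% too high

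*SAP*

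**What the plan says.** SAP 5.6 (Handling of Missing Data) gives one proration rule for the ADAS-Cog totals. The observed total is multiplied by one plus a ratio whose numerator is the "Maximum Score of the missing value" and whose denominator is the "Sum of the Maximum Score of the non - missing values". Three tables then print the factor item by item for ADAS-Cog11, ADAS-Cog13 and ADAS-Cog14. The rule is used when a single item is missing for non-cognitive reasons.

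In the ADAS-Cog-14 table, both the Word Recognition row and the Maze row read "Observed total*(1+12/78" (closing bracket follows). The row for all other questions reads "Observed total*(1+5/85" (likewise).

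The maximum for Maze can be found elsewhere in the same SAP:

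- Section 5.5 assigns "a conversion code of 0 to 5 for the digit cancellation and maze completion".
- Section 5.5 also says "The ADAS-Cog14 total score includes all of the items in the ADAS-Cog13 and the maze item".
- Section 5.6 gives the two ranges: "The ADAS-Cog-13 total score ranges from 0-85" and "The ADAS-Cog-14 total score ranges from 0-90".

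**The concern.** The Maze row carries the factor for an item with a maximum of 12, but Maze is scored 0 to 5. The general rule and the table therefore give different answers for a missing Maze item. A programmer working from the table would build in the larger factor, and a quality check of the program against the table would pass it.

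Higher ADAS-Cog scores mean more impairment. A Maze item missing only after baseline would thus add false worsening to the change score, relative to the SAP's own rule. One missing only at baseline would add false improvement and also distort the baseline covariate in the MMRM of SAP 9.3.

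ADAS-Cog14 has its own 6- and 12-month analysis tables and figures (SAP Appendix 2, 14.2.4) and enters the Pearson correlations in SAP 9.4. With 7 participants planned per arm (protocol 17.2), a single affected value can be seen in the arm mean.

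**Working it through.** **Item maxima, from SAP 5.5 and the tables in 5.6**

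- Word Recall 10, Orientation 8, Word Recognition 12, and eight other ADAS-Cog11 items at 5 each: 10 + 8 + 12 + 8×5 = 70, the stated ADAS-Cog11 maximum.
- Add Delayed Word Recall 10 and Number Cancellation 5: 70 + 10 + 5 = 85, the stated ADAS-Cog13 maximum.
- Add Maze 5: 85 + 5 = 90, the stated ADAS-Cog14 maximum.

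Maze has a maximum of 5 by two routes: the 0-to-5 code in SAP 5.5, and 90 − 85 = 5.

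**Rule:** factor = 1 + (maximum of missing item) / (sum of maxima of the remaining items).

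**Reproducing the ADAS-Cog-14 table**

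| Missing item | By the rule | Printed | Agrees |
|---|---|---|---|
| Word Recall | 1+10/80 = 1.1250 | 1+10/80 | yes |
| Orientation | 1+8/82 = 1.0976 | 1+8/82 | yes |
| Word Recognition | 1+12/78 = 1.1538 | 1+12/78 | yes |
| Delayed Word Recall | 1+10/80 = 1.1250 | 1+10/80 | yes |
| Maze | 1+5/85 = 1.0588 | 1+12/78 = 1.1538 | **no** |
| All other questions | 1+5/85 = 1.0588 | 1+5/85 | yes |

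Every row of the ADAS-Cog11 and ADAS-Cog13 tables also reproduces. The Maze row is the only one that does not.

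**Could another Maze maximum explain 12/78?** The 13 other items sum to 85 whatever Maze is worth, so the denominator must be 85. A Maze maximum of 12 would give 1+12/85 = 1.1412 and a scale total of 97, which matches neither the printed factor nor the stated range.

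**Size of the error**

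- Relative: (90/78) / (90/85) = 85/78 = 1.0897, so the imputed total is 9.0% too high.
- Absolute: (1.1538 − 1.0588) × observed total = 0.0950 × observed total.

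The observed totals below are illustrative; the documents give no expected ADAS-Cog14 scores.

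| Observed total, 13 items | Printed factor | Correct factor | Excess | Excess / 7 |
|---|---|---|---|---|
| 20 | 23.1 | 21.2 | 1.9 | 0.27 |
| 30 | 34.6 | 31.8 | 2.9 | 0.41 |
| 40 | 46.2 | 42.4 | 3.8 | 0.54 |

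The last column is the shift in a raw arm mean at one visit if one of 7 participants is affected.

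**Range check.** The printed factor credits Maze with observed total × 12/78. That passes the item's maximum of 5 once the observed total exceeds 5 × 78/12 = 32.5. The imputed total passes 90 once the observed total exceeds 90 × 78/90 = 78.

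**The case against.** The arithmetic is not in dispute; the case on the other side is about reach.

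- **Narrow trigger.** The row applies only when Maze is the sole missing item and the reason is non-cognitive. The documents give no rate for this, so one affected participant in an arm is a scenario, not a forecast. This stands.
- **Limited scope.** The primary objective is safety and tolerability, and SAP 5.5 names ADAS-Cog11 as the primary cognitive endpoint. ADAS-Cog11 and ADAS-Cog13 do not contain Maze. The Cognitive Composite has its own missing-data rule, and the Attention composite is not derived when Maze is missing. This also stands: the error is confined to the ADAS-Cog14 total and what is computed from it.
- **Dilution.** In a raw pooled mean of 14 active participants the shift halves, to about 0.14 to 0.27 points, and the model-based estimates in SAP 9.3 will not move by exactly the raw amount. If Maze is missing at both baseline and follow-up, most of the error cancels: what remains is 0.0950 × the change in the observed total. Both points are fair.
- **Plausible values at low scores.** At observed totals of 20 and 30 the printed factor implies Maze scores of 3.1 and 4.6, which a participant could obtain. The error is therefore one against the SAP's own rule, not proof that a given imputed value is far from the truth.
- **Protocol 17.9 rules out imputation altogether,** while SAP 11.8 reports no change from the protocol's planned analysis. On the protocol's wording the table would not operate. That conflict needs settling separately; it does not make the cell correct.

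These points limit the expected effect. None supplies a reading under which 1+12/78 is right for Maze.

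**Conclusion.** The concern holds. The Maze row of the ADAS-Cog-14 table contradicts the rule stated just above it and the item maximum stated in SAP 5.5. It appears to repeat the Word Recognition factor. Where it operates, it inflates the imputed ADAS-Cog14 total by 9.0%, or 0.095 times the observed total.

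The factor and the percentage follow from the SAP alone. The point sizes (1.9 to 3.8 per participant, 0.27 to 0.54 in a raw arm mean) rest on two assumptions: observed totals between 20 and 40, and one affected participant among 7 at a visit. How often the row will be used cannot be judged from the documents. Conclusions on safety, ADAS-Cog11, ADAS-Cog13, the z-score composites, imaging and CSF treatment comparisons are not touched; correlations that use the ADAS-Cog14 total could be.

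**What to change.** In SAP 5.6, in the ADAS-Cog-14 table, change the Maze factor to 1+5/85. Alternatively, delete the Maze row so that the item falls under the row for all other questions, which already carries that factor. Leave the Word Recognition row as it is: the same expression is correct there.

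The cost is one cell in the SAP and, if the derivation is already programmed, the matching line of code. No data collection, sample size or model changes.

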5.7. Coding Abbreviations

Any coding abbreviations used in data listings will be included in the key in a footnote, as appropriate.

6. ANALYSIS POPULATIONS

6.1. Safety Analysis Set

The safety analysis set will include all subjects who were administered with the investigational product (IP), including those who may have withdrawn prior to study completion.

Safety data will be presented for all subjects in the safety analysis set, and summarised by treatment group.

Subject disposition and background data, including demographics, relevant background, participation and compliance data, will be presented for all subjects in the safety analysis set.

Participants who are assigned a randomization number but withdraw prior to dosing will not be included in the safety analysis set. Available details of their participation and reason for withdrawal will be listed separately.

6.2. Efficacy Analysis Set

Efficacy data will be presented for all subjects who were administered with the IP, including those who may have withdrawn prior to study completion.

The full analysis set (FAS) for efficacy will include all subjects who receive IP and who have at least one post-dose assessment of any of the cognitive and clinical endpoints.

Summaries of efficacy assessments will be presented for the FAS analysis set, by treatment group.

6.3. Pharmacokinetics Analysis Set

Pharmacokinetic concentration data will be listed and presented graphically for all subjects who were administered with active IP, including those who may have withdrawn prior to study completion. Pre-dose trough plasma concentrations will be determined for all subjects IP in the pharmacokinetics analysis set, noting that this may be not applicable on a scheduled sampling day for subjects from whom PK sample collection was not completed.

The per protocol pharmacokinetic analysis set will include all subjects in the PK Analysis Set who have no major protocol violations that impact on pharmacokinetics. Subjects who do not complete the sampling per schedule, but pre-dose trough samples on at least one visit day (after Day 1), will be evaluated. Data from subjects who experience emesis on the day prior to pre-dose trough sample collection at, or before, two times the t_{max} observed in previous studies (2 hours post-dose) may be deleted from statistical analysis..

Summaries of concentration data will include only subjects in the per protocol pharmacokinetic analysis set. Pharmacokinetic concentration data will be summarised by treatment group.

6.4. Pharmacodynamic Analysis Set

Pharmacodynamic data will be presented for all subjects who were administered with IP, including those who may have withdrawn prior to study completion.

The per protocol pharmacodynamic analysis set will include all subjects who receive IP and who have at least one post-dose result for any CSF concentrations.

Summaries of pharmacodynamic assessments will be presented for the Pharmacodynamic analysis set, by treatment group.

7. SUBJECT DISPOSITION/BACKGROUND DATA

7.1. Subject Disposition

Subject disposition and administration procedures recorded in the CRF are as follows:

- Written informed consent
- Randomization
- Administration of IP
- Study completion /discontinuation
- Protocol deviations
- Additional comments

Details of participation and inclusion in analysis populations will be listed by subject. Completion status will be summarised by treatment group.

Details of administration of IP will be listed by subject. Exposure to IP will be summarised by treatment group.

Protocol deviations will be listed by subject. A summary of protocol deviations will be prepared for inclusion in the clinical study report.

7.2. Baseline and Eligibility Assessments

Baseline and eligibility assessments are as follows:

- Demographic details
- Medical, Surgical and Psychiatric history
- Physical examination
- Eligibility
- Serology (HIV, Hepatitis B and C)
- Pregnancy Tests
- Blood sampling for Apolipoprotein E (ApoE) genotyping
- Modified Hachinski exam
- Geriatric Depression Score (GDS)
- Alzheimer's Disease Diagnosis

7.3. Baseline Data Analysis

Demographics will be listed individually by subject and summarised by treatment group and overall.

Medical history and physical examination data at baseline and results of tests performed for eligibility will be listed by subject.

Baseline assessments of on-study measures will be listed and summarised along with post-dose assessments, as described below.

8. SAFETY DATA

8.1. Safety Assessments

Safety assessments are as follows:

- Adverse events and concomitant medications used:
 - Continuous monitoring throughout the study period
- Vital signs:
 - Body temperature, seated systolic and diastolic BP, pulse rate and respiratory rate
- Body mass
- Clinical laboratory tests:
 - Hematology - red blood cell count, erythrocyte mean corpuscular haemoglobin concentration (MCHC), erythrocyte mean corpuscular volume (MCV), hematocrit, hemoglobin, leukocyte count, and absolute counts of monocytes, neutrophils, basophils, eosinophils and platelets
 - Chemistry - glucose, calcium, albumin, total protein, sodium, potassium, bicarbonate, chloride, magnesium, BUN, creatinine, creatine kinase, alkaline phosphatase, ALT, AST, bilirubin, lipase, lactate dehydrogenase (LDH) and phosphorus
 - Coagulation –INR, prothrombin time.
 - Urinalysis – osmolality, creatinine, calcium, sodium, turbidity, color, specific gravity, pH, protein, glucose, ketones, bilirubin, blood, urobilinogen, nitrite, leukocytes, and microscopic particles
 - Thyroid Tests – TSH, T3, T4
- ECG (ventricular rate, PR, QRS, QT, QTcF (Fridericia's formula for correction), QTcB (Bazett's formula for correction))
- Physical examination including all major organ systems (exception: genitourinary and reproductive should be symptom-directed).
- Symptom Directed Neurological Examination
- Columbia Suicide Severity Rating Scale (C-SSRS)

8.2. Safety Data Presentation and Analysis

All clinical safety and tolerability data will be listed for each subject.

Safety data will be summarized using descriptive statistics. Where summaries include changes from baseline, the relevant baseline value will be determined as described in Section 5.5 above.

All treatment-emergent adverse events reported in this study will be listed using MedDRA terms, as coded per the Data Management Plan. The number of subjects reported with AEs and the number of AEs reported following administration of the IP will be summarised by treatment, grouped according to system organ class and preferred term, using descriptive statistics. The order for system organ class will be according to the Internationally Agreed Order, as per the guidance document MedDRA® *Data Retrieval and Presentation: Points to Consider*, specific to the MedDRA version used for this study. Summaries of AEs will also be presented by severity and by relationship to investigational product. In these summaries, subjects will be counted only once per MedDRA term, for the AE of highest severity or least favourable relationship. Summaries will also be presented of SAEs and of AEs leading to study withdrawal.

Clinical laboratory parameters for clinical chemistry, hematology, coagulation, urinalysis and thyroid tests will be listed and summarised by treatment group and study timepoint. Medical assessments of blood and urine parameters will be summarised by treatment group and study timepoint. A summary of changes from baseline will also be presented for serum clinical laboratory parameters. Individual subject profiles will be presented for any laboratory parameters with at least one post-dose value outside the laboratory's reference ranges and deemed clinically significant.

Vital signs will be listed and summarised by treatment and study timepoint. A summary of changes from pre-dose baseline will also be presented.

Body mass will be listed and summarised by treatment and study timepoint. In addition, a summary of changes from pre-dose baseline will be presented.

ECG parameters will be listed and summarised by treatment and study time point. A summary of changes from pre-dose baseline will also be presented. For QTcB the number of subjects with values greater than 450 (and 480, 500) msec or an increase from baseline of at least 30 (and 60) msec will also be presented, in accordance with ICH E14 (Note for guidance on the clinical evaluation of QT/QTc interval prolongation and proarrhythmic potential for non-antiarrhythmic drugs, CHMP/ICH/2/04).

Changes in physical examination findings over time will be listed by body system for each subject. It is noted that any untoward findings identified on physical examinations after the administration of the first dose of study medication will be captured as an adverse event if those findings meet the definition of an adverse event as defined in the protocol.

Changes in neurological examination findings over time will be listed by neurological system for each subject.

Changes in the Columbia Suicide Severity Rating Scale (C-SSRS) will be listed for each subject.

